**SCHEDULE OF EVENTS**

Protocol Activity	Screening	Induction/ Re-induction E (Days 1-75)							Consolidation J (Days 1-55)				Maintenance K (Days 1-28)	EOT	Follow-up
	≤ 28 days prior to D1	D1	D3	D5	D6	Weekly (+/- 2 days)	Induction response D20 (+1 day)	Remission evaluation D28 to D60	D1	D3	D4	Weekly (+/- 2 days)	D1 (+/- 7 days)	Within 7 days of last dose	Every 3 month (+/- 14 days)
Informed Consent A	X														
Clinical Evaluation and Procedures															
Eligibility Review	X														
Disease Classification	X														
Medical History	X														
Concomitant Medication Review	X	For the entire duration of study participation													
AE/ SAE Review		From when participant start study therapy on induction day 1 up until 28 days after the last dose of study therapy/ and until resolution of any treatment-related AE/ SAE													
Physical Exam	X	X				X			X			X	X	X	X
ECOG Performance	X	X				X			X			X	X	X	X
12-lead ECG	X				X G	X G,H					X G			X	
ECHO	X														
BMA/BMBX	X C						X	X				X N		X L	
MRD (send to UW)							X	X						X L	
Cytogenetics /Molecular profiling	X C						X	X						X L	

Research sample for gene expression correlatives	X C, D						X D	X D						X D,L	
HSCT information/ Survival Status															X M
Laboratory Assessments															
Hematology	X	X				X	X	X	X			X	X	X	X
Chemistry	X	X				X			X			X	X	X	
Urinalysis	X														
Coagulation	X														
Pregnancy Test B	X								X				X		
Study treatment															
CPX-351 Infusion		X	X	X F					X	X					
Glasdegib					X I						X I		X		

**Abbreviations:**

AE=Adverse Event, SAE=Serious Adverse Event, ECOG=Eastern Cooperative Oncology Group, ECG=Electrocardiogram, ECHO=Echocardiogram, BMA=Bone Marrow Aspirate, BMBX=Bone Marrow Biopsy, MRD=Minimal/Measurable Residual Disease, UW=University of Washington, HSCT=Hematopoietic Stem Cell Transplant, D=Day, EOT=End of Treatment

**Footnotes:**

- A Must be obtained before undergoing any protocol-specific study procedures, unless as part of standard of care
- B Serum beta-HCG should be done for any female of child-bearing potential
- C Bone marrow collections do not need to be repeated if a diagnostic bone marrow procedure was done prior to informed consent and is done within 28 days of starting day 1 of induction
- D Collect bone marrow aspirate for research sample for gene expression correlatives; if patient has any circulating blasts, then peripheral blood can be collected instead of aspirate; if bone marrow is a “dry tap,” then this sample does not need to be collected
- E Re-induction is based on response evaluation bone marrow done on day 20 of induction. If there is greater than 5% blast count, re-induction is recommended. The final decision for re-induction is based on investigator’s discretion. For patients who will be treated with re-induction, an ECHO and pregnancy test (for female patients of child-bearing potentials) will be done before starting re-induction
- F Omit CPX-351 on day 5 for participants receiving re-induction

G ECG is done pre-dose and can be done up to 24 hours before planned glasdegib dosing

H During induction, repeat an ECG a week after starting glasdegib (around day 13-15). If clinically significant abnormal ECG or clinically significant changes in QTc, then refer to section 6.4 for further guidance. If normal or non-clinically significant abnormalities and/or changes in QTc, additional ECG monitoring is not required and is done per the treating investigator's discretion

I Glasdegib should continue until day 1 of the next cycle of CPX-351

J Up to two cycles of consolidation is allowed. These are 28 day cycles, unless delays are necessary. In the case of a delay, glasdegib will continue daily until the start of CPX-351 infusion in the next cycle. If the patient will proceed to allogenic SCT, then consolidation can be skipped or shorten. Glasdegib will be stopped at least 7 days before transplant.

K These are 28 days cycle. Patients who are not receiving HSCT will be allowed to proceed to glasdegib maintenance for up to 1 year of study start

L At the time of suspected relapse, a bone marrow aspirate/ biopsy will be done and samples will be collected. Patients will discontinue glasdegib in anticipation of start of treatment for relapsed disease

M Patients who undergo HSCT will have their HSCT information collected and will only require survival follow up. No other procedures or requirements will be collected

N At the end of consolidation, a bone marrow biopsy is recommended but is not required by the protocol. If it is done, it is suggested to send for cytogenetics, molecular studies, and MRD.

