#### **7.1.16 Research samples**

Additional bone marrow aspirate or peripheral blood will be collected for gene expression testing.

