### **7.2 Procedures during Treatment**

#### **7.2.1 Induction**

- Physical exam will be done weekly
- Review previous and concomitant medications
- ECOG Performance Status Review
- Blood draws for laboratory studies will be done weekly
- ECGs will be done on day 6 before starting Glasdegib and approximately one week after day 6 (on day 13-15)
- Review of concomitant medications
- Adverse event assessment
- Assessment of minimal residual disease assessed by multi-parameter flow cytometry. This should be done according to local institutional guidelines.

- Bone marrow aspiration and biopsy
  - Day 20
  - Upon recovery of cytopenias typically around day 28 to 60, at the discretion of treating physician. If counts has not recovered by day 60, then complete on day 60.
- Additional BMA or PB will be collected for gene expression testing

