#### **Gene Expression**

For gene expression testing, 2 mL will be collected from the bone marrow biopsy sample. In the event that there is a dry tap, the gene expression sample will be collected using peripheral blood if there are any circulating blasts present. If there are no circulating blasts, the gene expression sample will not be collected for testing. The sample needs to be processed immediately and carefully handled. Sites are responsible for providing their own tubes and vials for collection of all research related samples. In the event that a site does not have funding for supplies, the sample will not be collected and will not be considered a deviation. All samples will be shipped to and stored at UCI Clinical Trials Biospecimen Laboratory until analysis, which will be done at another laboratory. Please refer to the study sample lab manual for further processing, storage, and shipment instructions.

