## **10.2 Complete remission**

Complete remission is defined as no circulating blasts or extramedullary disease with a bone marrow biopsy with trilineage hematopoiesis with less than 5% blasts and ANC greater/equal than 1,000/uL and platelet count greater/equal than 100,000/uL.

Refractory disease is the failure to achieve CR at the end of induction.

Progressive disease is the increase of at least 25% in the absolute number of circulating or bone marrow leukemic blasts or appearance of extramedullary disease.

Relapsed disease is the reappearance of blasts in the bone marrow (greater than 5%) or in the blood after achieving CR or CRi.

MRD negative CR is the absence of detectable leukemic blasts using multiparameter flow cytometry at the University of Washington.

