### **13.4.2.4 Gene Expression**

We will use differential gene-expression analysis to try to identify genes or sets of genes where change in expression levels correlate with response to study treatment.

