**Appendix E. IWG Response Criteria****International Working Group Response Criteria in AML**

Classification	Definition
Complete remission (CR)	Bone marrow blasts < 5 percent; absence of blasts with Auer rods; absence of extramedullary disease; ANC > 1000/ $\mu$ L; platelet count > 100,000/ $\mu$ L; independence of red cell transfusions
Complete remission with incomplete hematologic recovery (CRi)	All CR criteria except for residual thrombocytopenia (platelet counts < 100,000/ $\mu$ L) and neutropenia (ANC < 1000/ $\mu$ L)
Complete remission with partial hematologic recovery (CRp)*	Bone marrow blasts < 5 percent; absence of blasts with Auer rods; absence of extramedullary disease; ANC > 500/ $\mu$ L; platelet count > 50,000/ $\mu$ L; independence of red cell transfusions
Morphologic leukemic-free state	Bone marrow blasts < 5 percent; absence of blasts with Auer rods; absence of extramedullary disease; no hematologic recovery required
Partial remission (PR)	Relevant in the setting of phase I and II clinical trials only; all hematologic criteria of CR; decrease of bone marrow blast percentage to 5 to 25 percent; and decrease of pretreatment bone marrow blast percentage by at least 50 percent
Cytogenetic remission	Reversion to a normal karyotype at the time of morphologic CR (or CRi) in cases with an abnormal karyotype at the time of diagnosis; based on the evaluation of 20 metaphase cells from bone marrow
Molecular remission	No standard definition; depends on molecular target
Resistant disease	Failure to achieve CR or CRi (general practice; Phase 2/3 trials), or failure to achieve CR, CRi or PR (Phase 1 trials); only includes subjects surviving $\geq$ 7 days following completion of initial treatment, with evidence of persistent leukemia by blood and/or bone marrow examination
Death in aplasia	Deaths occurring $\geq$ 7 days following completion of initial treatment while cytopenic; with an aplastic or hypoplastic bone marrow obtained within 7 days of death, without evidence of persistent leukemia
Death from indeterminate cause	Deaths occurring before completion of therapy, or < 7 days following its completion; or deaths occurring $\geq$ 7 days following completion of initial therapy with no blasts in the blood, but no bone marrow examination available
Relapse	Bone marrow blasts $\geq$ 5 percent; or reappearance of blasts in the blood; or development of extramedullary disease

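### Conflicting rules on blood versus marrow for the gene-expression sample can tie tissue source to response, and the planned analysis of expression change takes no account of source

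*Combined protocol and SAP*

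**What the plan says.** The combined protocol and SAP gives three different rules for the source of the gene-expression sample.

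- **Schedule of Events, footnote D.** Aspirate is the default, but "if patient has any circulating blasts, then peripheral blood can be collected instead of aspirate". For a dry tap, "then this sample does not need to be collected".
- **Section 9.2, Gene Expression.** The sample comes from the marrow procedure. "In the event that there is a dry tap, the gene expression sample will be collected using peripheral blood if there are any circulating blasts". Where none circulate, no sample is taken.
- **Section 7.** Section 7.1.16 states: "Additional bone marrow aspirate or peripheral blood will be collected for gene expression testing". Section 7.2.1 states: "Additional BMA or PB will be collected for gene expression testing". Sections 7.2.6 and 7.3 do the same. None of them sets a condition on the choice.

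Two further passages connect source to outcome. Section 10.2: "Complete remission is defined as no circulating blasts or extramedullary disease". Section 13.4.2.4 plans differential expression analysis to find "genes or sets of genes where change in expression levels correlate with response to study treatment". That section does not mention the source of the sample.

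**The concern.** Expression measured in blood and in marrow may differ for reasons unrelated to treatment. If the source changes between baseline and follow-up more often in responders than in non-responders, a gene that differs between the two tissues will appear to change with response even when treatment has no effect on it. Footnote D makes such a pattern possible because it conditions the blood option on circulating blasts, and clearing them is part of the definition of remission.

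At stake is the exploratory objective on gene expression as a biomarker of response. Section 13.4.2.1 sets aside study-wise type 1 error control for secondary and ad-hoc analyses, so nothing in the plan would separate a tissue artefact from a signal. The documents mention no CRF field for sample source. If source is not captured at collection, it may be hard to recover at analysis.

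**Working it through.** **Step 1: where the rules conflict.**

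| Situation | Footnote D | Section 9.2 |
|---|---|---|
| Aspirate obtained, no circulating blasts | Marrow | Marrow |
| Aspirate obtained, circulating blasts | Marrow or blood | Marrow |
| Dry tap, circulating blasts | Sample may be omitted | Blood |
| Dry tap, no circulating blasts | No sample | No sample |

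The conflict is in the second and third rows. Section 7 sets no condition, so two sites can each follow the protocol and send different tissues from similar patients.

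**Step 2: which source is open to whom.** The Schedule of Events applies footnote D at screening, day 20, remission evaluation and end of treatment. Take a patient with circulating blasts whose screening sample was blood.

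- In CR at the remission evaluation, no blasts circulate (Section 10.2), so footnote D offers marrow only. The pair is blood then marrow.
- Not in remission and blasts still circulating, footnote D offers blood again. The pair may be blood then blood.
- Not in remission but no circulating blasts at that visit, marrow only. The pair is blood then marrow, as for a responder.

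The response endpoint is CR plus CRi (Section 2.2). CRi takes over the CR requirement only by reference (Appendix E: "All CR criteria except for residual thrombocytopenia" and neutropenia), and the Appendix E row for CR does not itself list circulating blasts. The explicit wording is in Section 10.2.

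**Step 3: illustration of size.** The plan gives no figure to reproduce. Inputs from the documents: 30 evaluable patients (Section 13.3) and 47% CR/CRi with CPX-351 (Section 1.5.3), so 0.47 × 30 = 14.1, taken as 14 responders and 16 non-responders. Assumed, because the documents do not give them:

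- one gene with no true association, unit SD at each time point with independent errors, and a two-sided 5% t-test on change;
- d, the blood-to-marrow difference in SD;
- q, the share of baseline samples that are blood, equal in both groups;
- p, the share of non-responders with baseline blood who give blood again;
- all responders give marrow at follow-up.

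The expected change caused by source alone is −d·q in responders and −d·q·(1 − p) in non-responders. The spurious difference, responders minus non-responders, is therefore −d·q·p. With q = 0.5 and p = 1 it is −0.5 SD at d = 1 and −1.0 SD at d = 2. With p = 0.5 it is −0.25 and −0.5. With p = 0 it is zero.

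Simulated false-positive rates at q = 0.5:

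| p | d = 1 SD | d = 2 SD |
|---|---|---|
| 100% | 15% | 39% |
| 50% | 7% | 13% |
| 25% | 6% | 7% |
| 0% | 5% | 5% |

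At p = 100%, a quarter of baseline samples from blood gives about 7% and 14%, and three quarters gives about 28% and 73%. With no tissue difference the rate is 5% throughout.

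**The case against.** The strongest reply is that the blood option is permissive and conditional. Aspirate is the default in footnote D as well as in Section 9.2, blood needs circulating blasts at that visit, and a non-responder can have residual marrow blasts with none in the blood. If few such patients give blood twice, little bias follows, as the lower rows of the table show. That stands. A reader might infer that the analysis will be biased, or that 15% and 39% are typical rates. The documents support only that it can be biased, and those two rates are the upper end over p for the assumed half-blood baseline.

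Two other stronger readings also go beyond the text. The first is that Section 9.2 says the opposite of footnote D throughout; in fact they agree when a dry tap comes with no circulating blasts, and both start from marrow. The second is that patients whose diagnostic marrow preceded consent (footnote C) can supply a baseline sample only from blood. Footnote C says the marrow need not be repeated. It does not say whether stored aspirate may be used or a repeat taken.

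It is also fair to say that the stakes are modest. The objective is exploratory, and Section 13.4.2.1 treats p-values as a guide. The correlative rationale in Sections 1.7 and 7.5 concerns expression and overall survival, which baseline samples can address without the source being set by later response. The laboratory manual cited in Section 9.2 is not among the documents and may contain rules on source. It would not remove the contradiction in the protocol text, nor the silence of Section 13.4.2.4.

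**Conclusion.** The concern holds as a structural risk. Footnote D, Section 9.2 and Section 7 do not agree on when blood may be sent, and following footnote D as written can confound tissue source with response in the Section 13.4.2.4 change analysis. On the illustrative assumptions, with half of baseline samples from blood, the per-gene false-positive rate runs from the nominal 5% to about 15% at a 1 SD tissue difference and 39% at 2 SD. The share of non-responders who give blood again decides where in that range it falls. Neither that share, nor the blood share at baseline, nor the tissue difference can be found in the documents. The EFS6 primary analysis and the safety analyses are not touched. The change is worth making because it is cheap and because source may not be recoverable later.

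**What to change.** 1. Reconcile footnote D, Section 9.2 and Sections 7.1.16, 7.2.1, 7.2.6 and 7.3 into one collection rule: aspirate is the sample at every marrow time point, and blood is a labelled fallback only when no research aspirate is available (a dry tap, or a pre-consent marrow with no usable aspirate).
2. Record sample source and blast percentage on the CRF for each gene-expression sample.
3. In Section 13.4.2.4, restrict the change analysis to same-source pairs and analyse baseline expression within source or adjusted for source.
4. Add a sensitivity analysis of change adjusted for blast percentage. Blast content falls in responders, so even marrow-to-marrow change follows response through cell mix, and matching on source alone does not deal with this.

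The cost is some protocol wording, two CRF fields and a few lines of analysis plan. No procedure is added, because a marrow is already scheduled at the day 20 and remission evaluations and at suspected relapse. The real price is fewer usable pairs: patients whose baseline sample is blood will mostly drop out of the change analysis, which matters with about 30 patients. They remain usable in the baseline analysis.

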### 2.1 Primary Objective/ Primary Endpoint

2.1.1 Primary Objective	2.1.2 Primary Endpoint

 
To determine the efficacy when using the combination of CPX-351 and Glasdegib to treat patients with newly diagnosed AML with MDS-related changes or treatment related AML
 
	
 
Efficacy will be measured by following the 6 month event-free survival (EFS). EFS is defined as the as the time from screening biopsy to the date of confirmed disease progression, relapse from CR/CRi, treatment failure, or death, whichever comes first. Of interest, a 6 month EFS will be important to follow
 

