## 2.2 Secondary Objectives/ Secondary Endpoints

2.2.1 Secondary Objectives	2.2.2 Secondary Endpoints

 
To evaluate any toxicities associated with the combination
 
	
 
Adverse events are to be captured and characterized by type, frequency, severity (as graded by NCI CTCAE v.5.0), timing, seriousness and relationship to study drugs
 

 
To evaluate the rate of response
 
	
 
The overall response rate (ORR) includes the rate of complete remission (CR) and complete remission with incomplete count recovery (CRi)
 

 
To evaluate the durability of response
 
	
 
Durability of response will be measured by relapse-free survival (RFS), defined as the amount of time a patient remains in remission after having achieved a CR or CRi
 

 
To evaluate survival and the length of survival
 
	
 
Survival follow up information will be collected to determine overall survival (OS)
 

 
To evaluate the time to return of normal hematopoiesis
 
	
 
Laboratory studies including complete blood counts (CBCs) will be collected to evaluate the recovery of bone marrow hematopoiesis
 

 
To evaluate the proportion of subjects who go on to receive allogeneic HSCT
 
	
 
HSCT information will be collected for patients who proceed to allogeneic HSCT
 

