### **5.7 Maintenance**

For patients who complete consolidation chemotherapy and not proceeding to allogeneic transplant, they will proceed to maintenance therapy. Glasdegib oral daily will be continued for up to one year. The patients will proceed with monthly assessments of disease status if they are on Glasdegib maintenance. If they are adults of child-bearing age and potential, they will need to be reminded of contraception. If they are a woman of child-bearing age and potential, they will need to have pregnancy test.

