## **5.9 Duration of Follow Up**

Patients will be followed every 3 months for one year after removal from or completion of treatment or death, whichever comes first. Patients removed from treatment for unacceptable adverse events will be followed until resolution or stabilization of the adverse event then for relapse and survival afterwards. Patients who undergo allogeneic stem cell transplant will only be followed for survival.

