#### **7.4 Follow-up Procedures**

Patients will be followed every 3 months for a minimum of one year after removal from or completion of treatment or death, whichever comes first. Patients who undergo allogeneic stem cell transplant will only be followed up for survival status. Patients removed from treatment for unacceptable adverse events will be followed until resolution or stabilization of the adverse event then for relapse and survival afterwards.

- Survival status (either in clinic during standard visit or by phone)
- Physical Exam
- ECOG Performance Status Review
- Blood draws for laboratory studies
- Bone marrow aspiration and biopsy
  - At any time of suspected relapsed disease, at the discretion of treating physician
- Assessment of minimal residual disease assessed by multi-parameter flow cytometry. This should be done according to local institutional guidelines.

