## **10.4 Event-free survival**

Event-free survival is defined as the time from screening biopsy to the date of confirmed disease progression, relapse from CR/CRi, treatment failure, or death, whichever comes first. This was chosen as an endpoint for several reasons. It is known to incorporate several endpoints of interest including efficacy of the treatment as well as toxicity that both contribute to the outcome of the patient. Complete remission may not capture the full benefits of Glasdegib since the drug may prevent relapse through different mechanisms than enhanced cytotoxicity.

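### Relapse after transplant counts as an EFS6 event, but the plan does not specify that it be collected, so EFS6 can be biased upward

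*Combined protocol and SAP*

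**What the plan says.** **Endpoint.** Section 2.1 ends the event-free interval at confirmed progression, "relapse from CR/CRi, treatment failure, or death, whichever comes first". Section 10.4 gives the same list: "the time from screening biopsy to the date of confirmed disease progression, relapse from CR/CRi, treatment failure, or death". Transplant is not on it. Section 13.2.2 refers back to 2.1 for the end of the interval.

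**Analysis.** Sections 13.2.1 and 13.2.3 treat EFS6 as a proportion of evaluable participants. The regimen passes if the exact one-sided 90% lower bound exceeds 0.5. Evaluability is defined for toxicity and safety (6.0, 11.2) but not for efficacy.

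**Follow-up after transplant.** Footnote M says transplanted patients "will have their HSCT information collected and will only require survival follow up. No other procedures or requirements will be collected". Section 5.9 says "Patients who undergo allogeneic stem cell transplant will only be followed for survival" and 7.4 says "Patients who undergo allogeneic stem cell transplant will only be followed up for survival status". Section 2.2 says only "HSCT information will be collected for patients who proceed to allogeneic HSCT", against the objective on the proportion transplanted.

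**Follow-up of others.** On maintenance, "The patients will proceed with monthly assessments of disease status if they are on Glasdegib maintenance" (5.7). Patients removed for toxicity are "followed until resolution or stabilization of the adverse event then for relapse and survival afterwards" (5.9).

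**Transplant rule.** The one rule, in 10.5, censors at the start of conditioning. It is written for overall survival.

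**The concern.** The endpoint and the follow-up plan do not match. The event list keeps a transplanted patient at risk of relapse up to month 6, but the follow-up rule asks only whether that patient is alive. A site that follows the plan exactly could record a patient who relapsed after transplant and survived to month 6 as event-free.

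That error runs one way, upward, and it falls on the quantity that decides whether the combination merits further study. It arises only in transplanted patients, because the plan names disease follow-up or relapse for the others. Transplant is a planned route out of remission in this trial. Relapse-free survival and duration of response share the gap.

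**Working it through.** **1. Can transplant precede month 6?** Section 5.6 lets a patient in remission with a donor go straight to transplant, and footnote J lets consolidation be skipped or shortened. The remission marrow falls between days 28 and 60. The clock starts at a biopsy that footnote C allows up to 28 days before day 1 (7.1 counts the 28 days from registration instead). Taking month 6 as day 183 from biopsy (assumption):

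- month 6 falls between treatment day 183 − 28 = 155 and day 183;
- after a day-28 remission marrow, 155 − 28 = 127 to 183 − 28 = 155 days remain.

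The glasdegib stop, donor arrangements, conditioning, transplant and any relapse must all fit within those days, so the period at risk after transplant is shorter. On slow paths transplant falls after month 6. Two consolidation cycles at the longest intervals in 5.4, with the second cycle also lasting 55 days, end 75 + 55 + 55 = 185 days after the last induction starts. For those patients the gap does not touch EFS6. Transplant before month 6 is therefore possible, but its frequency is not given.

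**2. Reproduce the plan's bounds.** The lower bound is the 10th percentile of Beta(x, n − x + 1). With n = 28 and x = 28p it gives 0.461, 0.511 and 0.563 for p = 60%, 65% and 70%. The table in 13.3 gives 46%, 51% and 56%, so it reproduces. (The 90% probability stated there does not: the exact value at a true 65% with 28 patients is 0.616. That is a separate matter and is not used here.)

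**3. Find the cut-offs.**

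| Event-free | Lower bound | Result |
|---|---|---|
| 19/30 | 0.4999 | fails |
| 20/30 | 0.534 | passes |
| 17/28 | 0.468 | fails |
| 18/28 | 0.504 | passes |

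At the cut-off, one misclassified patient changes the decision.

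**4. Illustrate the bias.** Suppose true EFS6 is 50% and an average of m relapses per trial are missed (assumption). The observed proportion then behaves as p = 0.5 + m/n. The false-positive rate is P(X ≥ 20) for n = 30 and P(X ≥ 18) for n = 28, with X binomial(n, p).

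| n | m = 0 | m = 1 |
|---|---|---|
| 30 | p = 0.500, rate 4.9% | p = 0.533, rate 9.9% |
| 28 | p = 0.500, rate 9.2% | p = 0.536, rate 17.2% |

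The two sizes differ at m = 0 because the exact test is conservative at 30 and uses nearly all of the nominal 10% at 28. With m = 0 there is no error.

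**The case against.** **A reader might infer that no rule classifies a transplanted patient**, so that they could equally be dropped or counted as failures, with error in either direction. The documents do not support this. The event list in 2.1 and 10.4 is closed and 13.2.2 points to it. Counting transplant as an event would contradict that list, and excluding these patients would need a rule that appears nowhere. What remains is smaller: evaluability is undefined for efficacy, and the censoring rule for overall survival might be carried across by analogy, although a plain exact proportion has no place for censored patients. One confirming sentence would close this.

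**A reader might infer that relapse will not be collected.** That goes too far. The content of the HSCT information is not given and the case report forms are not in the documents, so relapse may already be on the form. The supportable statement is that the plan does not specify it.

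**The contrast with other patients is less sharp than it looks.** Maintenance lists no scheduled marrow (7.2.8), and in follow-up marrow is taken on suspicion at the physician's discretion (7.4). Relapse detection depends on suspicion there too. Even so, relapse is asked about in those patients, whereas for transplanted patients the text restricts follow-up to survival.

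**A material effect is not shown.** This stands. At the accrual goal of 30, bias of one missed relapse leaves the false-positive rate inside 10%, and the example at the cut-off is the most sensitive case.

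**Conclusion.** The point holds as a mismatch between the primary endpoint and the follow-up that feeds it. Under the literal reading, any error from missed post-transplant relapse is upward. It requires a patient who was transplanted, relapsed and was still alive, all before month 6.

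The documents do not allow the size to be fixed. The 34% transplant figure in 1.5.3 comes from an earlier CPX-351 trial and carries no time window, so it is not used. The illustrative rates rest on two assumptions: a true EFS6 of exactly 50%, and missed relapses averaging one per trial. They show that the effect could matter at 28 evaluable patients and would stay within the nominal level at 30. They do not show that the trial's decision would be wrong. This is a cheap improvement, not a flaw that undermines the design.

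**What to change.** 1. Amend footnote M, 5.9 and 7.4. For transplanted patients, record relapse (yes/no), its date and the date last known in remission. Take these from the transplant record at the existing 3-monthly survival contact, up to the first contact on or after month 6.
2. State in 13.2, before data are reviewed, that EFS6 counts the listed events regardless of transplant and that transplanted patients stay in the denominator. Note why this differs from 10.5: the exact proportion in 13.2.3 needs a yes/no status for each patient.
3. Optionally, add a sensitivity analysis that censors EFS at the start of conditioning, a date 10.5 already requires, and reads month 6 from the Kaplan-Meier curve.

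**Cost.** A few case report form fields, if they are not already on the HSCT form, and some wording; no added procedure. EFS6 may come out slightly lower. Detection would still depend on each transplant centre's practice. EFS6 and overall survival would treat transplant differently, which the report must explain.
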